### **8.4. Safety Oversight**

A detailed overview of the roles and responsibilities, the safety process and timelines are detailed in the “Safety Monitoring Plan”.

## 9. STATISTICAL CONSIDERATIONS

### 9.1. Statistical and analytical plans

A Statistical Analysis Plan (SAP) will be prepared to precisely define the final statistical analysis of the data. The SAP will be based on the study protocol and will be in compliance with ICH E9.

### 9.2. Statistical Hypothesis

Only descriptive statistics will be used.

### 9.3. Analysis Datasets

A Safety Set will include all patients treated with study medication.

An Efficacy Set will include patients satisfying all inclusion criteria and none of the exclusion criteria and for whom any efficacy assessment is available.

### 9.4. Description of statistical methods

#### 9.4.1. General Approach

Descriptive statistics will be used throughout all the analyses.

Continuous variables will be summarized using the mean, standard deviation, median, and range.

Categorical variables will be summarized using frequency counts and percentages.

#### 9.4.2. Analysis of the (primary) safety endpoint(s)

AEs will be coded using Medical Dictionary for Regulatory Activities (MedDRA). The frequency, causal relationship, expectedness and severity of AEs and SAEs will be summarized for the overall study period and for the following treatment phases:

- Acute phase: IS till 6 weeks post-IS (V5 included)
- Long term phase: beyond 6 weeks post-IS (V5 excluded) till study completion (completion V8 or early termination whichever comes first)

Besides a listing including all SAEs and NVDX3 related AEs occurring between screening (V1) and 12-months post-IS (Primary endpoint) tables will be generated for:

- All TEAEs and SAEs summarized by System Organ Class (SOC) and Preferred Term (PT)
- All related TEAEs and SAEs (according to the Principal Investigator) summarized by SOC and PT
- All related TEAEs and SAEs (according to the sponsor) summarized by SOC and PT
- All TEAEs and SAEs summarized by SOC, PT, and highest severity
- All unexpected SAEs summarized by SOC and PT

- All AESIs and rAESIs summarized by SOC and PT

More details on the descriptive tables will be given in the SAP.

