**b) Relationship to the NVDX3 treatment**

All adverse events (AEs) must have their relationship to the NVDX3 treatment (relatedness to the NVDX3 implant, the NVDX3 implant procedure and other study or non-study related procedures) assessed by the Principal Investigator who examines and evaluates the patient based on the Investigator Brochure, the temporal relationship of the event and his/her clinical judgment. Alternative causes, such as underlying disease(s), concomitant therapy, and other risk factors will be considered and investigated. The degree of certainty about causality will be graded using the categories below.

For each AE/SAE, the Principal Investigator must document in the medical notes that he/she has reviewed the AE/SAE and has provided an assessment of causality.

There may be situations in which an SAE has occurred, and the Principal Investigator has minimal information to include in the initial report to the Sponsor. However, it is very important that the Principal Investigator always assesses the causality for every event before the initial transmission of the SAE data to the Sponsor. The Principal Investigator may change in the eCRF his/her opinion of causality in light of follow-up information: a SAE follow-up report with the updated causality assessment will be recorded in the eCRF.

As part of medical review, the causal relationship will also be assessed by the safety officer of the Sponsor or his delegate.

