1.3 Study Endpoints

1.3.1 Primary Endpoint

The primary endpoint is the evaluation of all SAEs and NVDX3 related AEs between screening (V1) and 12 months post-IS (V8).

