2.4.1.4 Related Adverse Events

For each type of causality (NVDX3, grafting surgery, other study procedure) an adverse event is considered related if it is assessed as possibly, probably or definitely related or if the assessment is missing.

An adverse event will be considered NVDX3-related only in case the causality is NVDX3. It is not NVDX3-related if the cause is the grafting surgery or other study procedure.

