2.4.1.5 Adverse Events of Special Interest (AESI)

The following adverse events will be considered as of special interest:

- Hypersensitivity reaction
- Immunological reaction
- An AE requiring immunosuppressive medication
- Ectopic bone formation
- Tumor formation
- Continued non-union/Non-fusion
- Refracture of the targeted area
- Revision surgery/intervention including removal of NVD-X3
- Any other condition considered by the treating physician as treatment failure

A reportable AESI (rAESI) is defined as an AESI that is assessed by the Principal Investigator as possibly, probably or definitely related to NVDX3.

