4.4.1 Adverse Events

The analysis of adverse events will consist of:

- An overview of treatment-emergent adverse events consisting of:
 - Any TEAE
 - Any serious TEAE
 - Any NVDX3-related TEAE
 - Any NVDX3-related serious TEAE
 - Any TEAE related to the grafting surgery, including the applied medical device
 - Any TEAE related to other study procedure
 - Any unexpected TEAE
 - Any unexpected serious TEAE
 - Any severe TEAE
 - Any severe serious TEAE
 - Any treatment-emergent AESI
 - Any treatment-emergent rAESI
- Frequency distributions and total number of events for patients with any TEAE by MedDRA SOC and by MedDRA SOC and PT.
- Frequency distributions and total number of events for patients with any NVDX3-related TEAE by MedDRA SOC and by MedDRA SOC and PT.
- Frequency distributions and total number of events for patients with any TEAE by MedDRA SOC and by MedDRA SOC and PT, and maximal severity.

Frequency distributions will be provided for the entire study period (all treatment-emergent events), and broken down into IS till 6 weeks post-IS (V5 included) (acute events) and beyond 6 weeks post-IS (V5 excluded) till study completion (completion V8 or early termination whichever comes first) (mid-term).

Separate listings will be provided for:

- Non-Treatment-Emergent AEs
- Acute or Mid-term TEAEs
- Serious TEAEs
- TEAEs of special interest

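### The SAP omits the protocol's sponsor-assessed related-event summary without declaring it, so no planned summary would show a non-serious AE that only the sponsor judges NVDX3-related

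*Protocol*

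**What the plan says.** **Protocol.** Section 8.1.7, under relationship to the NVDX3 treatment, has the Principal Investigator assess causality for every AE. It adds that, within medical review, "the causal relationship will also be assessed by the safety officer of the Sponsor or his delegate". Section 9.4.2 then asks for two separate tables: "All related TEAEs and SAEs (according to the Principal Investigator) summarized by SOC and PT" and "All related TEAEs and SAEs (according to the sponsor) summarized by SOC and PT". It also asks for a listing of all SAEs and NVDX3-related AEs as the primary-endpoint output, and leaves further table detail to the SAP.

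**SAP.** Section 1.3.1 states: "The primary endpoint is the evaluation of all SAEs and NVDX3 related AEs", from screening to 12 months. Section 2.4.1.4 handles each type of causality (NVDX3, grafting surgery, other study procedure) and says "an adverse event is considered related if it is assessed as possibly, probably or definitely related or if the assessment is missing", naming no assessor. Section 2.4.1.5 does name one, but only for reportable AESIs: "assessed by the Principal Investigator as possibly, probably or definitely related to NVDX3". Section 4.4.1 plans one related-event table: "Frequency distributions and total number of events for patients with any NVDX3-related TEAE by MedDRA SOC and by MedDRA SOC and PT". It adds overview rows for NVDX3-related TEAEs and NVDX3-related serious TEAEs, again with no assessor. Section 3.6 declares one AE table as dropped, the SAE table by SOC, PT and maximal severity. It says nothing about the sponsor-assessed table.

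**The concern.** The protocol placed the sponsor's causality view among the analyses of the primary safety endpoint, next to the investigator's. A programmer who follows the SAP would produce only one of the two, and a reader of SAP 3.6 would not learn that the other had been removed.

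What is lost is the comparison. This is a first-in-human, open, single-arm study in which implant and fixation surgery take place in one operation, and the protocol's risk section lists infection both for the product (at the implant site) and for surgery in general (local infection). Attribution is therefore a matter of judgement, and two assessors can reasonably differ. SAEs enter the primary endpoint whatever their cause. A non-serious AE enters only if it is judged NVDX3-related, so disagreement matters there. Where the investigator says unrelated and the sponsor says related, no table, overview row or named listing in the SAP is planned to show it.

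**Working it through.** The plan states no figure to reproduce; the study is descriptive and has no formal sample size calculation. The check is a comparison of texts, followed by a short illustration of size.

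**1. The six table groups in Protocol 9.4.2 against SAP 4.4.1 and 3.6**

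| Protocol 9.4.2 | SAP 4.4.1 | Declared in SAP 3.6? |
|---|---|---|
| All TEAEs and SAEs by SOC/PT | TEAE table kept; serious TEAEs have an overview row and a listing | not needed for TEAEs |
| Related, by investigator | one NVDX3-related TEAE table, assessor not named | not needed if this is the investigator's |
| Related, by sponsor | no table, overview row or named listing | no |
| By SOC/PT and highest severity | TEAE table kept | SAE version declared dropped |
| Unexpected SAEs by SOC/PT | overview row only | no |
| AESIs and rAESIs by SOC/PT | overview rows and an AESI listing | no |

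Three groups are absent as tables and undeclared. Two of them (unexpected SAEs; AESIs and rAESIs) keep overview rows, and their events also fall in the all-TEAE table. These are documentation points only. The sponsor-assessed group is the one with nothing left in its place.

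**2. Which events are affected**

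- Serious events are in the primary endpoint regardless of cause, so only their related label can differ.
- Non-serious, investigator related: already in the NVDX3-related table.
- Non-serious, investigator unrelated, sponsor related: in the all-TEAE table and the TEAE listing, but shown as related in no planned summary. This is the gap.

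**3. Size per patient**

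The target is 10 evaluable patients, evaluable meaning implanted (Protocol 4.3), so the Safety Set is 10 if recruitment meets its target. A patient whose only NVDX3-related event is one that the sponsor alone so judges moves the incidence by 1/10 = 10 percentage points; two such patients move it by 20 points and three by 30.

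For scale, exact (Clopper-Pearson) 95% intervals, which the SAP does not plan for categorical data:

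- 0/10: upper limit 1 − 0.025^(1/10) = 0.308, so 0 to 30.8%
- 1/10: lower limit 1 − 0.975^(1/10) = 0.0025; upper limit 0.445, so 0.3 to 44.5%
- 2/10: 2.5 to 55.6%

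**4. How often (assumption only)**

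Let d be the chance that a patient has an event only the sponsor calls NVDX3-related and none that the investigator does. With independent patients, the chance of at least one such patient in 10 is 1 − (1 − d)^10:

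- d = 0: 0
- d = 1%: 1 − 0.99^10 = 10%
- d = 2%: 1 − 0.98^10 = 18%
- d = 5%: 1 − 0.95^10 = 40%
- d = 10%: 1 − 0.90^10 = 65%

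The documents give no value for d. These figures show only that the answer depends on it.

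**The case against.** **The assessor is clear enough.** A reader might infer that the related count in the primary endpoint depends on an unstated choice between two assessors. The documents do not support that. Protocol 8.1.7 makes the investigator the main assessor, Protocol 8.2.4 lists the investigator's assessment among the AE data collected, and both documents define reportable AESIs by the investigator's view. The SAP is built on the annotated CRF, so its causality items are most naturally the investigator's. The AE item list in SAP 2.4.1 is also partly blacked out and may name the assessor. Naming the assessor in the SAP is a helpful label for an evident default. This objection stands.

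**Nothing is hidden.** A reader might also infer that disputed events would vanish from the report. They would not. All TEAEs are tabulated by SOC and PT and listed, events related to the grafting surgery have an overview row, and Protocol 9.4.7 adds individual listings. The primary endpoint is a descriptive evaluation whose protocol output is a listing; no test or decision rule uses a related-AE rate. This stands too. What is lost is a summary of the sponsor's judgement. A sponsor field may appear in a listing, since listing columns are not given.

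**The infection example is weaker than it looks.** SAP 2.4.1.4 assesses each type of causality, and a rating of possibly related is enough, so an infection rated possibly related to both implant and surgery can count as NVDX3-related. The section's closing sentence, "It is not NVDX3-related if the cause is the grafting surgery or other study procedure", is open to an either/or reading but does not compel it. The example works only where one assessor rates NVDX3 itself as unrelated.

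**The SAP may refine the tables.** Protocol 9.4.2 leaves detail to the SAP. That permits elaboration, not an unrecorded removal, particularly when SAP 3.6 records the removal of a different AE table. The SAP's undertaking to explain changes in the study report covers only changes made after the SAP is final. This objection does not remove the point.

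**Conclusion.** The two documents conflict on one planned safety summary. The protocol requires the sponsor's causality assessment and a table of it; the SAP plans no such summary and does not say so. That conclusion rests on SAP 3.6 and 4.4.1, which show no redaction on this matter, and needs no assumption about how often the assessors disagree.

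The consequence is limited. No planned summary would show a non-serious AE that the sponsor alone judges NVDX3-related. Each patient affected only in this way would be worth 10 percentage points of related-AE incidence, assuming 10 patients in the Safety Set. Whether any such patient will occur cannot be judged from the documents; if the assessors always agree, the two summaries are identical. No hypothesis test is affected and no event is lost from the listings. It is still worth correcting, because in a first-in-human study a disagreement about product causality is informative and the protocol had arranged to show it.

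**What to change.** In SAP 4.4.1, present NVDX3-related TEAEs and NVDX3-related serious TEAEs with two columns, investigator and sponsor, as Protocol 9.4.2 foresees. List each event on which they differ. Label the investigator's assessment as the one used for the primary endpoint. State how a missing sponsor assessment is shown, since the rule that missing counts as related does not say which of two assessments it refers to.

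If the sponsor-assessed summary is to stay out, declare and justify that in SAP 3.6. The same section can record that the SOC/PT tables of unexpected SAEs and of AESIs/rAESIs are dropped, or they can be restored.

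The cost is SAP wording and one extra column in a small table. The protocol already requires the sponsor's assessment, so no amendment, visit or image is needed. If that assessment sits only in the safety database, it must be transferred before lock. The report would carry two related counts and would need a sentence to explain them.

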#### **9.4.3. Analysis of the secondary endpoint(s)**

The analysis of secondary endpoints will be described in the SAP (same for exploratory endpoints)

#### **9.4.4. Analysis of the exploratory endpoint(s)**

[REDACTED]

#### **9.4.5. Baseline and follow-up descriptive statistics**

Descriptive baseline characteristics will be listed.

Concomitant medications will be tabulated and listed by International Nonproprietary Names (INN). Additionally, pain medication will also be listed separately in view of its importance for the clinical outcomes.

#### **9.4.6. Planned interim analyses**

Safety and efficacy analysis might be performed as needed on a patient-by-patient level. Interim descriptive study analysis can be initiated to support safety, scientific and regulatory needs at any time

#### **9.4.7. Tabulation of individual response data**

Individual patient data listings will be produced in accordance with ICH/E3 guidelines.

### **9.5. Sample size**

No formal sample size calculation has been performed for this study since no formal hypothesis will have to be tested. However, as this is an early phase Proof of Concept study, the number of patients was limited to 10 individuals.

### **9.6. Measures to minimize bias**

To minimize bias, some potential variables have been standardized:

- Centralized Image Reading
- Maximum 2 sites, one orthopedic surgeon per site performing the intervention (limit large inter-site and inter-surgeon variabilities)
- Implant surgery:
  - The applied surgical technique and type of osteosynthesis devices has been standardized
  - Maximum volume of NVDX3 is fixed

## 10. CLINICAL MONITORING

Site monitoring is conducted to ensure that the rights and well-being of trial patients are protected, that the reported trial data are accurate, complete, and verifiable, and that the conduct of the trial is in compliance with the currently approved protocol/amendment(s), with ICH E6 GCP current version including GCP for ATMPs and with applicable regulatory requirement(s).

The Sponsor's monitor or representative is responsible for the eCRF review at regular intervals throughout the trial to ensure adherence to the protocol and all applicable regulations on the conduct of clinical research. The monitor should have access to patients' medical records and any other study -related records needed to verify the entries in the eCRF.

The investigator(s)/institution(s) will permit trial-related monitoring, audits, IEC review, and regulatory inspection(s), providing direct access to source data/documents.

It is important that the Principal Investigator and other trial personnel are available during the monitoring visits and that sufficient time is devoted to the process. The Principal Investigator agrees to cooperate with the monitor to ensure that any problems detected during the course of these monitoring visits are resolved.

Details of site monitoring are documented in a Trial Monitoring Plan (TMP). The TMP describes in detail who will conduct the monitoring, at what frequency monitoring will be done, at what level of detail monitoring will be performed, and the distribution of monitoring reports.

Independent audits may be conducted to ensure monitoring practices are performed consistently across all participating sites and that monitors are following the TMP.

## 11. SOURCE DOCUMENTS AND ACCESS TO SOURCE DATA/DOCUMENTS

### Source documents

Source documents (paper or electronic) are those in which patient data are recorded and documented for the first time, including any copies of transcriptions that are certified as per GCP definition after verification as being accurate and complete.

Data collection is the responsibility of the clinical trial staff at the site under the supervision of the Principal Investigator. The Principal Investigator is responsible for ensuring the timeliness of the data reported and ensuring that the source data are attributable, legible, contemporaneous, original, accurate, and complete (ALCOAC principles) to ensure accurate interpretation of data. The Principal Investigator must list the location and the responsible person for the collection of the source data that will be used for data entry in the eCRF. This list must be signed and dated by the Principal Investigator before the start of the screening period.

If required, in order to support the sites, hardcopies of the trial visit worksheets may be developed by the site for use as source document worksheets for recording data for each patient enrolled in the trial if not collected in the medical file. Data recorded in the electronic case report form (eCRF) derived from source documents should be consistent with the data recorded on the source documents.

The following data are source data in addition to the regular patient's medical file:

- Signed informed consent form (ICF)
- Printouts of electronic devices
- Laboratory reports
- Study logs

The scope of the Source Data Verification (SDV) is regulated in the Trial Monitoring Plan set up for this clinical trial. Source documents that are required to verify the validity and completeness of data entered in the eCRFs must not be obliterated or destroyed.

The electronic clinical data system includes password protection and internal quality checks, such as automatic range checks, to identify data that appear inconsistent, incomplete, or inaccurate.

### Use of a site electronic system

When clinical observations are entered directly into a site's computerized medical record system (e.g. in lieu of original hardcopy records, which is not the Sponsor's eCRF), the electronic record can serve as the source document if the system has been validated in accordance with health authority requirements pertaining to computerized systems used in clinical research. An acceptable computerized data collection system allows preservation of the original entry of data. If original data are modified, the system should maintain a viewable audit trail that shows the original data as well as the reason for the change, name of the person making the change, and date of the change.

PI should provide adequate documented evidence on the validation process for electronic computerized systems used at hospital.

## 12. QUALITY CONTROL AND QUALITY ASSURANCE

The Sponsor is committed to ensure internal quality management of trial conduct, data and biological specimen collection, documentation and completion in accordance with the Quality Management System.

### Quality Control (QC)

QC procedures will be implemented beginning with the data entry system and data QC checks that will be run on the database will be generated. Any missing data or data anomalies will be communicated to the site(s) for clarification/resolution.

Following written Standard Operating Procedures (SOPs), the monitors will verify that the clinical trial is conducted, and data are generated (including radiological image acquisitions) and biological specimens are collected, documented (recorded), and reported in compliance with the protocol, with ICH E6 GCP current version including GCP for ATMPs and with applicable regulatory requirement(s).

The site will provide direct access to all trial related source data/documents, and reports for the purpose of monitoring and auditing by the Sponsor, and inspection by local and regulatory authorities.

In addition, an individualized quality management plan is developed for each Service Provider contracted by the Sponsor for the management of the trial.

### Quality Assurance (QA)

ICH E6 GCP guidelines state that independent audits and inspections of clinical trials should be performed based on risk assessment. It is the responsibility of the Principal Investigator and trial staff to ensure all trial related documentation is filed accurately and to make this available to the Sponsor or designee, regulatory agencies, providing direct access to source data/documents.

### On-Site Audits

In accordance with ICH E6 GCP and the Sponsor or designee's audit plans, this trial may be selected for an audit. Inspection of site facilities (e.g. drug storage areas, laboratories) and review of trial related records may occur in order to evaluate the trial conduct and compliance with the protocol, ICH E6 GCP, and applicable regulatory requirements.

The Principal Investigator will permit an independent audit by an auditor mandated by the Sponsor, after reasonable notice. An audit or a regulatory inspection is intended to determine if the trial was conducted as per protocol, ICH E6 GCP, and applicable regulatory requirements; if the rights and well-being of the patients were protected; and if the data relevant for the evaluation of the Investigational Medicinal Product (IMP) were captured, processed and reported in compliance with the planned arrangements.

Regulatory authorities may perform an inspection of the trial until several years after its completion. As for an audit, the Principal Investigator will permit a direct access to all trial documents, IMP accountability records, source records, and source data. If an inspection is announced, the Sponsor must be informed without delay (by addressing this occurrence to [REDACTED]).

